9.8. Vulnerable Populations

There is no intention to recruit individuals in vulnerable populations. More specifically, children or minors, and pregnant women, are expressly excluded from this clinical investigation. However, it is important to note that it is expected that a proportion of the sample population will be considered elderly or immunocompromised, as these individuals would generally constitute a large proportion of the PAP therapy user population. There will be no direct health-related benefit to this subgroup of the overall sample. PAP therapy does not serve as treatment for a health

problem specific to the elderly or immunocompromised, but it is imperative to ensure that the investigational product can be used effectively in this population. Therefore, recruitment will not specifically target this population, but will not exclude them from the sample should they meet the inclusion and exclusion criteria. There are no additional risks posed to elderly or immunocompromised participants that they are not already exposed to as routine users of PAP therapy.

9.9. Risks and Benefits

PAP therapy is considered standard treatment for the management of OSA. The risks associated with this treatment are limited to potential minor discomfort associated with using any type of PAP therapy mask during sleep, as documented in [REDACTED]. There will be no additional risks to participants undergoing the intervention over the course of this clinical investigation, as participants will be following routine practice for management of their diagnosed medical condition. Participants in the clinical investigation may benefit from receiving additional follow-up during appointments at [REDACTED], or advice regarding sleep disorders or PAP therapy. [REDACTED]

10. Clinical Investigation Design

10.1. Study Design

10.2. Controls and Bias

No control group will be used in the clinical investigation as it is designed to test the [REDACTED] the investigational product against product requirements, and potentially to inform future product development with findings. However, participants using specifically targeted released PAP therapy masks that are available to purchase on the market will be enrolled in the clinical investigation to fulfil the primary recruitment goals and provide comparison to the [REDACTED]. Therefore, while this is not a formal control group, there is a degree of control for comparison.

The investigational product is distinguishable and will be labelled with identifying features. Since the investigational product being tested is the same for the entire sample population, the clinical investigation will not be blinded. All participants recruited for this clinical investigation will receive a [REDACTED] for use in the home. Thus, there is only one treatment group and there will be no randomization as there is no intention to make comparisons between any treatment groups. Data collected across several research variables for this clinical investigation is qualitative in nature or self-reported. Where possible, objective and validated measurement tools have also been included to corroborate or elucidate any bias, or challenge and confirm conflicting or inconsistent data.

10.3. Data Collection

Treatment efficacy data will be derived from AHI and leak information in compliance reports, as collected by [REDACTED] during recruitment, [REDACTED] and prior to the [REDACTED]. Baseline data will be downloaded for a two-week period within 30 days prior to enrolment, and investigational data will be downloaded for all nights from Visit 1 to the night before participants attend [REDACTED].

To mitigate any risks associated with introducing another potential extraneous variable, participants will not be issued with a loan PAP therapy device. Participants will continue to use their usual PAP therapy device, with the introduction of the investigational product being the only intervention for the clinical investigation. This is unless the participant meets all inclusion and exclusion criteria, expect the exclusion criteria which specifies that the participant must use a PAP therapy device which possesses data recording capabilities to capture AHI and leak information that is accessible to

[REDACTED]. In such cases, the participant will receive a loaned a PAP therapy device with data recording capabilities from [REDACTED] if one is available, to use for the duration of the clinical investigation.

[REDACTED]

When leak is considered exceptionally high, the flow signal measured by devices can be disrupted, resulting in inaccurate residual AHI reporting. To counteract this, leak data will be analyzed on a nightly basis during both the baseline and intervention period.

[REDACTED]

Leak Threshold	Justification
20 L/min	A study looked to characterize leak profiles to investigate a correlation between leak rate and clinical outcomes. The study used the 20 L/min threshold as a call for action from the sleep technologists to refit the mask during a polysomnography study, since measures above this flow rate interfered with polysomnographic signals. ¹⁸
21 L/min	A study which investigated the effect of leak on ventilatory support and sleep architecture, found the 21 L/min flow rate to mark the threshold below which patients had improved oxygenation, decreased arousal index and an increase in rapid eye movement sleep. ¹⁹
24 L/min	Published American Association of Sleep Medicine guideline parameters for successful unattended titration of APAP, deemed 24 L/min of mask leak as the acceptable amount of leak over 5 hours of treatment for APAP devices for treating adults with OSA. ²⁰

10.4. Testing Conditions

During this clinical investigation, fittings with the [REDACTED] and interviews with participants will be conducted at [REDACTED] no special conditions. Participants will use the [REDACTED] mask in place of their usual PAP therapy mask in a home environment or in settings where they sleep over the course of this clinical investigation.

10.5. Equipment

Aside from the investigational product and the associated components included within each packaged [REDACTED] bag issued to participants at [REDACTED] still and video camera, laptop, caliper, nasal depth measurement guide, and disinfectant cleaning wipes, will be necessary to carry out the activities detailed in this CIP. Participants will be expected to bring their usual mask and PAP therapy device to Visit 1 and Visit 2. All equipment will be shipped via courier from [REDACTED] before the clinical investigation commences. This equipment, in addition to a portion of clinical investigation documentation, will be [REDACTED] once the clinical investigation ends. The following equipment will be used during this clinical investigation.

Item	Quantity	Purpose
[REDACTED]	1	[REDACTED]

10.6. Participant Compensation

[REDACTED]

10.7. Informed Consent

F&P maintains a standard operating procedure for documenting the expected informed consent process, 'Obtaining Informed Consent', which can be used if the investigation site does not maintain its own. A copy will be provided to the investigation site for review [REDACTED]

10.8. Case Report Form

This clinical investigation will utilize electronic CRFs [REDACTED]

[REDACTED] Only research personnel listed in the DOA are allowed to amend or make entries into the CRF.

10.9. Protocol Deviations

All deviations from the CIP shall be recorded together with an explanation. Deviations shall be reported to F&P in a timely manner and through the appropriate channels. [REDACTED]

[REDACTED] Where appropriate, deviations will be reported to the relevant IRB, competent authorities, or appropriate regulatory bodies. All deviations should be documented in the CRF for individual participants, or as a note to file to be included in the regulatory binder.

[figure not shown]
10.10. Event Timeline

Details of the key events that will occur during the clinical investigation are summarized below:

[figure not shown]
A.

The follow will take place during recruitment:

Procedures that will be carried out at [REDACTED] are detailed below, and will be noted in the individual CRF for each participant:

C. [REDACTED]

D. [REDACTED]

E. [REDACTED]

F. [REDACTED]

G. [REDACTED]

H. [REDACTED]

Note that any steps marked with an asterisk (*) above are optional. Participants can opt into these activities, but they do not have to complete them necessarily to continue in the clinical investigation. If audio or video recording occurs, activities conducted in all steps will be recorded until reimbursement is issued.

[REDACTED]

Consenting activities planned to occur during recruitment may take place at Visit 1, depending on the availability of participants and ability to confirm enrolment eligibility due the first pre-screening phone call.

For the purpose of conducting fitting assessments with the [REDACTED] mask, the PAP therapy device used by participants will be adjusted to match the prescribed pressure setting, as per the following:

- For participants using APAP, this will be their average pressure for F&P devices, their median pressure if on a ResMed device, and their mean pressure if on a Philips Respiration device
- For participants using BPAP, this will be their IPAP
- For participants using CPAP, this will be their prescribed fixed pressure
- For participants where their usual pressure is unknown, the pressure will be set at a fixed pressure of 10 cmH₂O

10.11. Roles and Responsibilities

[REDACTED]

10.12. Withdrawal Criteria

Participants will be informed that they have the right to withdraw from the clinical investigation at any time, without prejudice or compromise to their medical care, and are not obliged to state their reasons. [REDACTED]

[REDACTED] Participants are informed that they can return to using their usual mask for PAP therapy during the clinical investigation if they have reason to do so. Withdrawal can occur in person at the investigation site, or by phone call or email. Upon withdrawal, the participant will be informed to immediately stop using the investigational product and to return all associated items and packaging to the investigation site at their earliest convenience. In the event of a participant being withdrawn during a scheduled or unscheduled visit at the investigation site, the investigational product will be retrieved from the participant. Thereafter, participants will no longer be considered active in the clinical investigation. If the PI elects to withdraw a participant, the same procedure for investigational product reconciliation will be followed, and where serious or emergent medical attention is required, the PI will follow the usual emergency code of practice instituted at the investigation site.

The PI may withdraw a participant at any time for the following reasons:

- Protocol violation
- Safety concerns
- Serious illness
- AEs

Data from withdrawn participants may be used when results of the clinical investigation are analyzed if it is complete and accurate. If data from withdrawn participants is not used, [REDACTED] Participants will not be replaced after all original recruits have been attended their first appointment at the investigation site. If participants withdraw before this, another participant can be recruited as a replacement.

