12.1. Description of Statistical Design

The statistical design of this clinical investigation is aimed at evaluating the product requirements as defined by the respective [REDACTED] mask is safe and effective prior to its release into global markets and to support regulatory clearance applications where required. Therefore, the statistical design of this clinical investigation is considerate of its objectives and endpoints being confirmatory in nature, rather than exploratory, or in the pilot stage. [REDACTED]

[figure not shown]
Data from participant questionnaires and compliance reports will be saved in supporting folders of the [REDACTED] [REDACTED] For each participant and requirement, it will be determined if these have been met individually based on the acceptance criteria. Minitab will be used to perform a one-sided one-proportion test on each requirement using the corresponding confidence limit to confirm that the acceptance criteria has been met.

Details are as follows:

- H_0 : Proportion = Reliability Limit
- H_1 : Proportion > Reliability Limit
- Acceptance criteria: $P \leq 0.05$ to reject H_0

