12.4. Selection Criteria

Data from all participants who use the investigational product as part of this clinical investigation will be included in the analysis, unless a clear reason for exclusion is present, such as definitive proof the participant was not using the investigational product during the intervention period. Any data points that are excluded will be documented clearly with the reason for their exclusion. For participants who have withdrawn, all data collected up to the point of withdrawal may be used in the analysis, provided the data is complete and accurate.

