13.3. Adverse Events

An AE is any adverse change from the baseline condition of a participant, and is considered as any unfavorable and unintended symptom or disease that occurs over the course of the clinical investigation, whether related or unrelated to use of the investigational product or PAP therapy. All clinically significant AEs that occur during the clinical investigation that were not present prior to commencement of the clinical investigation, will be recorded in the CRF of the affected participant, and followed up by the PI until resolution or stabilization of the condition among participants occurs in accordance with GCP. The collection of AE data will commence once the participant is fitted with the investigational product at Visit [REDACTED] and up to 24 hours after the investigational product is returned at [REDACTED]

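### Section 10.12 lets a participant who has already used the mask be replaced, and the wording on withdrawn data then lets that person's failure drop out of the one-proportion tests unnoticed

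*Combined protocol and SAP*

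**What the plan says.** Section 10.12 sets the end of replacement by an event in the whole cohort: "Participants will not be replaced after all original recruits have been attended their first appointment at the investigation site". It continues: "If participants withdraw before this, another participant can be recruited as a replacement". No visible condition refers to the person's own fitting, use of the mask or reason for leaving. Adverse events and safety concerns are among the reasons for which the investigator may withdraw someone.

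Section 10.3 starts the intervention data at the first visit: "investigational data will be downloaded for all nights from Visit 1 to the night before participants attend" the later visit. Section 13.3 ties adverse event collection to fitting: "The collection of AE data will commence once the participant is fitted with the investigational product at Visit" (visit number redacted). Section 9.6 gives 40 to 45 recruits.

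On the analysis set, section 12.4 opens with a firm default: "Data from all participants who use the investigational product as part of this clinical investigation will be included in the analysis", unless there is a clear reason to exclude, and exclusions must be documented. For people who withdraw, the wording softens: "all data collected up to the point of withdrawal may be used in the analysis, provided the data is complete and accurate". Section 10.12 says much the same: "Data from withdrawn participants may be used when results of the clinical investigation are analyzed if it is complete and accurate". The sentence after that, on data that are not used, is partly redacted.

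Section 12.1 sets the test: "Minitab will be used to perform a one-sided one-proportion test on each requirement", passing at P ≤ 0.05 against a reliability limit that is not visible.

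**The concern.** Unless all first appointments fall together, early recruits have nights at home on the mask before the last recruit is seen. Section 10.13 expects skin reactions to an incompatible mask to appear soon after first use, so some mask-related withdrawals may come while replacement is still open. Two people with the same bad experience are then treated differently because of their place in the queue.

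The statistical danger comes from combining this rule with the discretionary wording on withdrawn data. Someone who stops after a few nights is the least likely to have data judged complete, and no visible rule scores that person as not meeting a requirement. If the person is set aside and a new recruit takes the place, the study still reports a full cohort of 40 to 45. The tests are one-sided and meant as confirmatory, the study is open-label with one arm, and the judgement is made with the outcome known. Leaving out failures can only push the pass proportion up.

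**Working it through.** The visible text gives no reliability limit, power or dropout rate, so there is no figure of the plan's own to reproduce. What follows shows which element causes the bias and how large it could be.

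**Inputs.** From the plan: one-sided test, alpha 0.05 (12.1); N = 45, the top of the range (9.6). Assumed: limit and true pass rate both p = 0.80; share of fitted participants who quit as failures, q = 0.05 or 0.10; share of those who quit before the cut-off, f = 0.5 or 0.8. Exact binomial tails throughout.

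**Step 1: reference.** The smallest passing count is 41 of 45, and P(X ≥ 41 | 45, 0.80) = 0.038. This is the false-pass rate with nobody left out.

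**Step 2: pass rate among those retained.** If the early quitters, a share d = q × f, are left out, the pass rate among the rest is p / (1 − d). It is the same with or without replacement.

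**Step 3: false-pass rate under three ways of handling the early quitters.**

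- A, replaced and excluded: X ~ Binomial(45, p/(1 − d)); P(X ≥ 41).
- B, excluded and not replaced: m ~ Binomial(45, 1 − d) remain; the test is run on m with its own critical value.
- C, replaced but counted: recruitment continues until 45 are retained; with K people replaced, the test is run on 45 + K with those K as failures.

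| q | f | d | p/(1 − d) | A | B | C |
|---|---|---|---|---|---|---|
| 0.05 | 0.5 | 0.025 | 0.80/0.975 = 0.821 | 7.5% | 6.7% | 3.6% |
| 0.05 | 0.8 | 0.040 | 0.80/0.960 = 0.833 | 11.0% | 8.8% | 3.4% |
| 0.10 | 0.5 | 0.050 | 0.80/0.950 = 0.842 | 14.1% | 10.7% | 3.3% |
| 0.10 | 0.8 | 0.080 | 0.80/0.920 = 0.870 | 28.5% | 21.1% | 3.1% |

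Column C stays below 5%: replacement with everyone counted does no harm. Column B exceeds 5% with no replacement at all. Exclusion alone accounts for (6.7 − 3.8)/(7.5 − 3.8) = 78% of the excess in the first row and (21.1 − 3.8)/(28.5 − 3.8) = 70% in the last. Replacement adds the rest.

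**Step 4: one data set.** Suppose three early failures are replaced and left out, and 41 of the 45 retained pass: 41/45 = 91.1%, p = 0.038, a pass. With the three counted: 41/48 = 85.4%, p = 0.229, a fail.

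**Step 5: other limits.** For limits from 0.60 to 0.90 and N = 40 or 45, the false-pass rate with nobody left out is 0.009 to 0.049. If up to one failure is dropped and redrawn once, it is 0.046 to 0.118; if up to two, 0.080 to 0.225.

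**The case against.** The strongest reply is that section 12.4 already answers the point. A person who was fitted and used the mask falls within the all-users set, the example given for exclusion is proof of non-use, and every exclusion must be documented. Section 11.2 also requires reasons for withdrawal to be recorded, and follow-up where possible when the mask's performance or safety is the cause. Applied firmly, with such people scored as failures, these rules give column C and no inflation. This stands as a partial safeguard. It does not close the gap, because the same section makes use of withdrawn participants' data optional and conditional on completeness, and no visible rule says how to score them.

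A reader might infer that replacing exposed participants in itself raises the pass proportion. The documents and the arithmetic do not support that: the effect needs exclusion as well, and exclusion without replacement produces most of it. A reader might also infer that the plan intends to drop early quitters. It does not say so, and its default points the other way.

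Redaction limits the point too. The appointment schedule is hidden, and if first appointments were clustered over a few days, few people would be exposed before the cut-off. That fitting takes place at the first appointment is inferred from sections 10.3 and 13.3. The redacted clause in 10.12 may govern exactly the case at issue.

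**Conclusion.** The point holds as a gap created by two rules together. Section 10.12 allows a participant who has used the mask to be replaced, and the discretionary wording in 10.12 and 12.4 allows that person's result to be left out. When both happen, the one-sided tests lean towards passing and the restored cohort size conceals it.

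Under the assumed limit of 0.80 and the assumed quit rates, the false-pass rate moves from 3.8% to between 7.5% and 28.5%. These figures are illustrations and a worst case, since every early quitter is taken to be a failure, replaced and excluded. They are not estimates for this trial, and the visible text does not show how many participants could be affected. Confidence is high about what the replacement rule permits and low about the size of its effect. The change is worth making because it is cheap and the tests are confirmatory.

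**What to change.** Make two changes together. Amending 10.12 alone would leave the exclusion route, and most of the bias, in place.

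1. **Section 10.12.** Allow replacement only for a participant who withdraws before his or her own fitting with the investigational mask. Once fitted, a participant is not replaced, whatever the stage of recruitment.
2. **Section 12.4.** Keep every fitted participant, including anyone already replaced, in the denominator of each one-proportion test. Count a participant who withdraws for a mask-related reason without evaluable data as not meeting the requirement. Apply this always, not only when a replacement has occurred, and bring the optional wording on withdrawn data in 10.12 and 12.4 into line with it.

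The cost is a few sentences, possibly slightly fewer completers, and a slightly lower observed pass proportion. The 40 to 45 range leaves some room for early withdrawals. Neither change affects a participant's care or right to withdraw.

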10.13. Follow-up Plan

[figure not shown]
All participants are free to receive standard care from their medical provider or healthcare professional throughout and after the completion of the clinical investigation. Participants will be followed up with throughout the duration of their enrolment in the clinical investigation, defined as the date informed consent is completed up to the date the participant either attends their final appointment at the investigation site or is formally withdrawn. [REDACTED]

[REDACTED], participants will be obliged to report any AEs or SAEs for 24 hours after either their last use of the investigational product or their last contact with the investigation site for the purposes of the clinical investigation, regardless of whether they have completed the clinical investigation or have been withdrawn. There will be no active follow-up during this period, but participants will be informed of the requirement to report any AEs appropriately. This 24-hour period is deemed acceptable because once the investigational product is no longer in contact with the participant, there is no mechanism for new AEs

related to the intervention to occur. Moreover, as the investigational product does not interact with internal systems or structures of the body and there are no metabolization risks or anticipated residual impacts on the individual. The most obvious risks associated with PAP therapy mask use which is incompatible with the user, such as reddening, itching, or swelling of the skin, generally appear quickly upon initial application of the medical device, but will subside when use is discontinued.

